Title of Study: A PRospective OpEn-Label MuLticenter Study usIng the RhinAer[®] ProcEdure for Treatment of Subjects SuFfering with Chronic Rhinitis -RELIEF **Purpose:** The purpose of this study is to assess the clinical use of the RhinAer Stylus to treat tissue in the posterior nasal nerve area to improve symptoms in adults diagnosed with chronic rhinitis. **Indications for** The RhinAer Stylus is indicated for use in otorhinolaryngology (ENT) Use (United surgery for the destruction of soft tissue in the nasal airway, including in States): posterior nasal nerve regions in patients with chronic rhinitis. The Aerin Console is an electrosurgical system intended to generate radiofrequency electrical current for the use of an Aerin Medical Stylus. The Aerin Console is indicated for use in small clinic, office or hospital environments. Intended and The RhinAer Stylus is intended to improve nasal breathing by modifying the soft tissues of the nasal airway. It is indicated for use in **Indications for** Use (European otorhinolaryngology (ENT) surgery for the destruction of soft tissue in Union): the nasal airway, including in posterior nasal nerve regions in patients with chronic rhinitis. Device has CE Marking in EU. The Aerin Console is an electrosurgical system intended to generate radiofrequency (RF) electrical current for modification of soft tissues during ear, nose and throat procedures, when used with an Aerin Medical Stylus. It is indicated for use in delivering radio-frequency energy to tissues as part of ear, nose and throat procedures in small clinic, office or hospital environments. RhinAer The RhinAer procedure will be performed in the study clinic using the **Treatment:** RhinAer Stylus and Aerin Console. The RhinAer Stylus is a disposable handheld device capable of delivering bipolar radiofrequency energy to tissue when connected to the Aerin Console radiofrequency generating device. Participants will have both nostrils treated in the portion of the nasal cavity mucosa overlying the region of the posterior nasal nerve (the posterior middle meatus and posterior inferior meatus) during a single study procedure session. Each nasal cavity will be treated at 1, 2, 3, 4, or 5 nonoverlapping positions depending on the size of the target treatment area. Treatment settings to be used are temperature 60° C, power 4 watts, treatment time 12 seconds, and cooling time 0 seconds. **Study Design:** The study is designed as a multicenter (up to 20 sites), prospective, openlabel, single-arm study.

RhinAer RELIEF single arm protocol Rev C Final 27JAN2021CONFIDENTIAL

All participants will be evaluated prior to treatment and following treatment at week 13 (3 months). The 3-month evaluation will be used for the primary endpoint analysis.

The study will have an extended follow-up phase with evaluations conducted at 26 weeks (6 months), 52 weeks (12 months), 104 weeks (24 months) and 156 weeks (36 months) to provide additional information on longer-term efficacy and duration of treatment effect.

StudyThe primary objective is to assess the performance of the RhinAerObjective:procedure with respect to mean change in the 24-hour reflective Total
Nasal Symptom Score (rTNSS) at 3 months posttreatment when used as
a treatment for chronic rhinitis. A secondary objective is the evaluation
of treatment effect duration through an extended follow-up to 36 months.

PrimaryMean change in the 24-hour rTNSS from baseline to 3 months after the**Endpoint:**study procedure.

- Participant responder percentage, defined as the proportion of participants achieving a successful outcome at the 3-month evaluation. A successful outcome is defined as a 30% improvement (decrease) in the rTNSS.
 - Mean change in the Mini Rhinoconjunctivitis Quality of Life Questionnaire (MiniRQLQ) score from baseline to 3 months after the study procedure.
 - Frequency of device-related and procedure-related serious adverse events through the 3-month evaluation.

OtherAdverse events - Incidence (type and category) of adverse events overallOutcomeand by follow-up interval.

Measures: Nasal Assessment – The target posterior nasal nerve area within each nostril will be visually assessed at baseline, following the treatment procedure and at 3 months. The use of an endoscope for visual assessment is required. Representative still photographs or video of each nostril will be captured for each assessment.

Visual analog scale (VAS) for pain - perception of pain associated with the procedure on a 0 to 100 mm scale (0 indicating no pain and 100 indicating the worst pain ever) assessed posttreatment and at 3 months.

rTNSS:

- rTNSS mean and change from baseline at the 3-, 6-, 12-, 24- and 36-month follow-up evaluations.
- rTNSS Individual Nasal Symptom Scores (rhinorrhea, nasal congestion, nasal itching, and sneezing) at baseline and at the 3-, 6-, 12-, 24-month and 36-month follow-up evaluations.

• Proportion of responders based on improvement in rTNSS at the 3-, 6-, 12-,24-and 36-month follow-up evaluations.

MiniRQLQ:

- MiniRQLQ mean and change from baseline at the 3-, 6-, 12-, 24-, and 36-month follow-up evaluations.
- MiniRQLQ domain scores (activity limitations, practical problems, nose symptoms, eye symptoms, and other symptoms) at baseline and the 3-, 6-, 12-, 24-, and 36-month follow-up evaluations.

Participant satisfaction assessment - Five-question self-reported survey of satisfaction with the procedure and recommendation to others administered at the 3-, 6-, 12-, 24-, and 36-month follow-up evaluations.

Other rhinitis symptoms - current symptoms of cough and postnasal drip or excess mucous in the throat, rated on a 0 to 3 scale from 'No symptoms' to 'Severe symptoms', assessed at baseline and the 3-, 6-, 12-, 24-, and 36-month follow-up evaluations.

Change in amount of "as needed" medication/device use for chronic rhinitis symptoms - Self-reported assessment of an increase, no change, or decrease in medications and/or devices being used for treatment of symptoms compared to use prior to the procedure administered at the 3-, 6-, 12-, 24-, and 36-month follow-up evaluations.

Medications - Medications associated with relief or treatment of nasal airway obstruction symptoms will be documented at baseline and updated as necessary at each evaluation. In addition, medications associated with treatment of adverse events will be documented.

Length of The primary outcome will be evaluated at 3 months. In addition, evaluations at 6, 12, 24, and 36 months after treatment will extend follow-up to 3 years for evaluation of longer-term efficacy. Enrollment is anticipated to be completed within 6 months. Therefore, total study duration is anticipated to be approximately 42 months.

Study Centers: up to 20

Criteria:

- Participants: Up to 140 subjects
- Inclusion 1. Age 18 to 85 years (inclusively).
 - 2. Willing and able to provide informed consent.
 - 3. Willing and able to comply with the subject-specific requirements outlined in the Study Protocol.

	4.	Seeking treatment for chronic rhinitis symptoms of at least 6 months duration and willing to undergo an office-based procedure.
	5.	Moderate to severe symptoms of rhinorrhea (rTNSS rating of 2 or 3 for rhinorrhea).
	6.	Mild to severe symptoms of nasal congestion (rTNSS rating of 1, 2 or 3 for congestion).
	7.	$rTNSS \ge 6.$
Exclusion Criteria:	1.	Anatomic obstructions that in the investigator's opinion limit access to the posterior nasal passage.
	2.	Altered anatomy of the posterior nose as a result of prior sinus or nasal surgery or injury.
	3.	Active nasal or sinus infection.
	4.	History of significant dry eye.
	5.	History of any of the following: chronic epistaxis, documented episodes of significant nose bleeds in the past 3 months, rhinitis medicamentosa, head or neck irradiation.
	6.	Have rhinitis symptoms only on a seasonal basis due to allergies.
	7.	Known or suspected allergies or contraindications to the anesthetic agents and/or antibiotic medications to be used during the study procedure session.
	8.	Known or suspected to be pregnant or is lactating.
	9.	Participating in another clinical research study.
	10.	Has any condition that predisposes to excessive bleeding.
	11.	Is taking anticoagulants (eg, warfarin, Plavix) or 325 mg aspirin that cannot be discontinued before the procedure.
	12.	Has previous procedure or surgery for chronic rhinitis.
	13.	Other medical conditions which in the opinion of the investigator would predispose the subject to poor wound healing, increased surgical risk, or poor compliance with the requirements of the study.

Schedule	of Events
----------	-----------

		Treatment		Follow-up				
				In office Remote				
	Screening	Procedure	Immediate Postprocedure	3 Months ¹ (13 weeks)	6 Months (26 weeks)	12 Months (52 weeks)	24 Months (104 weeks)	36 Months (156 weeks)
Window (days)	(-30)	(0)	(0)	(± 14)	(± 30)	(± 30)	(± 30)	(± 30)
Activity / Assessment								
Eligibility	Х							
Consent	Х							
Demographics / Medical History	Х							
Physician Evaluations								
Nasal assessment (physical, endoscopic)	Х	Х	Х	Х				
Current medication use (study relevant)	Х	Х	Х	Х	Х	Х	Х	Х
Participant Evaluations								
VAS nasal pain			Х	Х				
Rhinitis symptoms (rTNSS, cough, and postnasal drip)	Х			Х	Х	Х	Х	Х
MiniRQLQ	Х			Х	Х	Х	Х	Х
Participant Satisfaction Survey				Х	Х	Х	Х	Х
Adverse Events	Х	Х	Х	Х	Х	Х	Х	Х

¹Primary analysis endpoint.

List of Abbreviations

ADE – Adverse Device Effect

AE – Adverse Event

ANOVA – analysis of variance

AR - allergic rhinitis

BMI – Body Mass Index

CONSORT - Consolidated Standards of Reporting Trials

CRF (eCRF) – Case Report Form (electronic Case Report Form)

CTA - Clinical Trial Agreement

EC - Ethics Committee

EDC – Electronic data capture

ENT – Ear, Nose, Throat; medical field of otorhinolaryngology (otolaryngology)

EU – European Union

FDA – Food and Drug Administration (US)

FWA - Federalwide Assurance for the Protection of Human Subjects

GCP - Good Clinical Practice

ICH – International Council for Harmonisation of Technical Requirements for Pharmaceuticals for Human Use

ICMJE -- International Committee of Medical Journal Editors

IFU – Instructions for Use

IRB -- Institutional Review Board

ISO - International Organization for Standardization

MCID - minimal clinically important difference

MDD - Medical Device Directive

MiniRQLQ - Mini Rhinoconjunctivitis Quality of Life Questionnaire

- NAR nonallergic rhinitis
- PNN posterior nasal nerve
- PRN Pro Re Nata (as needed or as required)
- RF Radiofrequency
- RFTR Radiofrequency turbinate reduction
- rTNSS Total Nasal Symptom Score (r, reflective)
- SADE Serious Adverse Device Effect
- SAE Serious Adverse Event
- SD standard deviation
- UADE (USADE) Unanticipated (Serious) Adverse Device Effect
- VAS Visual Analog Scale

1.0 Introduction and Background

Rhinitis is a condition in which the membrane lining the nasal cavity becomes irritated and swollen. Patients typically present with complaints of congestion, runny nose, sneezing, nasal itching, irritated throat, and postnasal discharge. The 2 major classifications of rhinitis are allergic rhinitis (AR) and nonallergic rhinitis (NAR). AR may be caused by allergens such as pollen, pet dander, mold, or dust. NAR may result from triggers that include chemicals, irritants, and medications.¹

Chronic rhinitis may significantly impact a patient's quality of life by causing fatigue, headache, and sleep disturbance, resulting in cognitive impairment and diminished productivity, and thereby posing both a personal and financial burden.²

The nasal cavity is covered with an epithelial lining made of cells which interact to serve appropriate functions in the nasal environment.³ Cells located in the epithelial lining include ciliated cells, goblet cells and seromucous glands. The goblet cell produces a carbohydrate called mucin which attracts water and forms a gelatin-like substance better known as mucus.^{3,4} The goblet cell is the most prominent mucus producing cell in the nasal membrane and, together with the seromucous glands, works to provide mucus to the nasal mucosal surface. The purpose of mucus is to protect the body from substances that can enter through the nasal cavity. Secretion is stimulated by dust or foreign substances that enter the nasal passage. Mucus is cleared by movement of the cilia and disposed to the stomach.⁴ Regulation of the seromucous glands and mucosal blood supply occurs through parasympathetic and adrenergic stimulation via the vidian nerve, posterior nasal nerves and other nerves. In some situations, the mucosa may become hyperresponsive to stimuli and produce excess mucus, resulting in rhinorrhea or postnasal discharge.

Patients presenting with runny or congested nose, watery eyes, irritated throat, and/or sneezing symptoms are evaluated to understand the types of triggers that may prompt the symptoms experienced. Understanding the patient's respiratory irritants may help differentiate between allergic or nonallergic responses.^{2,5,6} Physicians can observe the nasal structures by transnasal endoscopy to rule out anatomic conditions mimicking rhinitis. Common anatomical obstructions that may cause rhinitis-like symptoms are nasal polyps, deviated septum, foreign bodies, nasal tumors and turbinate hypertropy.^{1,2} Treatment of these anatomical causes, if present, may relieve rhinitis symptoms. The most common methods to determine allergy sensitivity are percutaneous skin testing and the allergen-specific immunoglobulin E (IgE) antibody testing. These tests can identify allergens the patient should avoid. However, if an allergic cause is eliminated through this testing, a diagnosis of nonallergic rhinitis could be made.^{1,2}

Treatment to reduce symptoms may include nasal irrigation (nasal lavage) multiple times a day with a saline rinse, use of over-the-counter oral or nasal antihistamines and/or corticosteroid sprays, and allergen immunotherapy in AR patients. Patients with nonallergic rhinitis are less likely to respond to oral antihistamines, but may find their symptoms relieved with intranasal antihistamine, corticosteroid, or anticholinergic sprays. Patients whose symptoms are not adequately relieved with conservative treatment often seek treatment to alleviate symptoms and may be candidates for nasal surgery. Vidian neurectomy is a surgical option to relieve chronic rhinitis symptoms as the vidian nerve supplies autonomic input to the nasal mucosa (as well as the palate and the lacrimal gland). While this surgery has been performed for over 50 years, it is controversial since access to the nerve can be technically difficult and complications with numerous surrounding important structures can occur.^{7,8} Common procedural side effects include dry eyes, nasal dryness or crusting and mild pain. More significant risks may include hemorrhage, vision loss and palate/lip/cheek numbness. In addition, improvement in symptoms is often unpredictable.⁷ An alternative neurectomy target is the posterior nasal nerve (PNN). The advantage of the PNN over the vidian nerve is its more limited innervation and activity on the nasal mucosa and its physical distance from other major nerve structures. As a result, complications associated with PNN surgery are less significant and occur less frequently than those described for vidian neurectomy,⁷ while still providing significant improvement in quality of life.⁹ A recent development is use of a cryosurgical probe to ablate PNN tissue.¹⁰ Significant improvement from baseline in Total Nasal Symptom Score (TNSS) using this cryosurgical probe was observed.

Radiofrequency (RF) energy has been used for decades in the fields of otorhinolaryngology, neurosurgery, cardiology, urology and general surgery. ENT surgeons currently use radiofrequency energy in numerous nasal therapies, including radiofrequency turbinate reduction (RFTR), which is a minimally invasive surgical option that can reduce tissue volume in a precise, targeted manner. There have been multiple studies analyzing the safety and outcomes of using radiofrequency energy in the RFTR procedure.¹¹ The technique is well tolerated and effective. Numerous studies have also demonstrated that radiofrequency tissue therapy in the nasal passage can be safe and effective in improving nasal obstruction and in preserving nasal function.¹² Aerin Medical's radiofrequency system using the Vivaer[®] ARC Stylus has been investigated and shown effective in treatment of nasal airway obstruction.¹³

Aerin Medical previously conducted a small feasibility study (TP220) using the Aerin Medical radiofrequency system to treat subjects with chronic rhinitis. The InSeca[®] Stylus was used to apply radiofrequency energy to the inferior turbinate in the PNN area. At 6-months post procedure, 73% of subjects showed improvement in their Sino-Nasal Outcomes (SNOT-22) score. There were no device-related or procedure-related serious adverse events.

The feasibility study was followed by a prospective, nonrandomized multicenter study (TP668) with 50 participants that supported regulatory clearance of the RhinAer Stylus for treating rhinitis by targeting treatment to the portion of the inferior turbinate mucosa overlying the region of the PNN. The mean reflective Total Nasal Symptom Score (rTNSS) at baseline was 8.5 (SD 1.8) and improved to 3.4 (SD 2.3) at the 12-week primary endpoint (5.1-point or 59.2% improvement). The responder percent for at least a 1-point improvement in rTNSS at 12 weeks was 94%. Responder percent, based on at least 2-, 3- (~30%), and 4-point improvements in rTNSS were 92%, 88%, and 69%. Patient reported satisfaction with the procedure and quality of life improvement were high. No serious adverse events related to the device were observed and the limited number of adverse events possibly associated with the procedure or device were

RhinAer RELIEF single arm protocol Rev C Final 27JAN2021CONFIDENTIAL

relatively mild, transient, and not unexpected for this type of procedure. Together, the safety and efficacy results demonstrated the benefits of treating the PNN area of the nasal passageway with RF using the Aerin Medical procedure for relief of chronic rhinitis.

The current study is proposed to provide additional evidence for the effectiveness of the RF procedure.

2.0 Purpose

The purpose of this study is to assess the clinical use of the RhinAer Stylus to treat tissue in the posterior nasal nerve area to improve symptoms in adults diagnosed with chronic rhinitis.

2.1 Device and Regulatory Status

The RhinAer procedure will be performed in the study clinic using the RhinAer Stylus and Aerin Console. The RhinAer Stylus is a disposable handheld device capable of delivering bipolar radiofrequency energy to tissue when connected to the Aerin Console radiofrequency generating device.

The RhinAer Stylus was cleared for use in the United States (US) by the Food and Drug Administration (FDA) under 510(k) K192471 and the Aerin Console was cleared under 510(k) K162810. The RhinAer Stylus is has CE Marking in the European Union (EU). The Aerin Console has CE Marking in the EU.

2.2 Indications for Use (US)

The RhinAer Stylus is indicated for use in otorhinolaryngology (ENT) surgery for the destruction of soft tissue in the nasal airway, including in posterior nasal nerve regions in patients with chronic rhinitis.

The Aerin Console is an electrosurgical system intended to generate radiofrequency electrical current for the use of an Aerin Medical Stylus. The Aerin Console is indicated for use in small clinic, office or hospital environments.

2.3 Intended Use and Indications for Use (EU)

The RhinAer Stylus is intended to improve nasal breathing by modifying the soft tissues of the nasal airway. It is indicated for use in otorhinolaryngology (ENT) surgery for the destruction of soft tissue in the nasal airway, including in posterior nasal nerve regions in patients with chronic rhinitis. RhinAer Stylus has CE Marking in the EU.

The Aerin Console is an electrosurgical system intended to generate radiofrequency (RF) electrical current for modification of soft tissues during ear, nose and throat procedures, when used with an Aerin Medical Stylus. It is indicated for use in delivering radio-frequency energy to tissues as part of ear, nose and throat procedures in small clinic, office or hospital environments.

2.4 Rationale

Patients suffering from symptoms attributed to chronic rhinitis have treatment options ranging from medications to surgical procedures that have varying degrees of effectiveness, discomfort, and potential complications. There remains a significant need for a simple, safe, nonsurgical, minimally invasive treatment that can provide sustained relief for patients suffering with symptoms of chronic rhinitis. The RhinAer procedure using RF technology has been shown to be safe, effective and durable in a single-arm trial comparing pretreatment condition with posttreatment condition. This study is being undertaken to provide additional evidence of the effectiveness of the procedure.

3.0 Study Objectives

3.1 Primary Objective

The primary objective is to assess the performance of the RhinAer procedure with respect to improvement in the rTNSS from baseline to 3 months when used as a treatment for chronic rhinitis.

The primary objective will be assessed through evaluation of the primary endpoint defined as comparison of the mean rTNSS at baseline to the mean rTNSS at 3 months postprocedure.

3.2 Secondary Objectives

Additional objectives include assessment and comparison of secondary endpoints and informational outcome measures.

Secondary endpoints are:

- Participant responder percentage at 3 months. Individual participant success (responder) is defined as at least 30% improvement (decrease) in the 24-hour reflective Total Nasal Symptom Score (rTNSS).
- Mean change in the Mini Rhinoconjunctivitis Quality of Life Questionnaire (MiniRQLQ) score from baseline to 3 months after the study procedure.
- Frequency of device-related and procedure-related serious adverse events through the 3-month evaluation.

Informational outcomes include:

- Adverse events Incidence (type and category) of adverse events overall and by follow-up interval.
- Nasal Assessment The target PNN area within each nostril will be visually assessed at baseline and following the treatment procedure at all evaluations. The use of an endoscope for visual assessment is required. Representative still photographs or video of each nostril will be captured at each visit.

RhinAer RELIEF single arm protocol Rev C Final 27JAN2021CONFIDENTIAL

- Visual analog scale (VAS) for pain perception of pain associated with the procedure on a 0 to 100 mm scale with 0 indicating no pain and 100 indicating the worst pain ever posttreatment through 3 months.
- rTNSS:
 - rTNSS mean and change from baseline at the 3-, 6-, 12-, 24-, and 36month follow-up evaluations.
 - rTNSS Individual Nasal Symptom Scores (rhinorrhea, nasal congestion, nasal itching, and sneezing) at baseline and the 3-, 6-, 12-, 24-, and 36-month follow-up evaluations.
 - Proportion of responders based on improvement in rTNSS at the 3-, 6-, 12-, 24-, and 36-month follow-up evaluations.
- MiniRQLQ:
 - MiniRQLQ mean and change from baseline at the 3-, 6-, 12-, 24-, and 36-month follow-up evaluation.
 - MiniRQLQ domain scores (activity limitations, practical problems, nose symptoms, eye symptoms, and other symptoms) at baseline and the 3-, 6-, 12-, 24-, and 36-month follow-up evaluations.
- Participant satisfaction assessment Five-question self-reported survey of satisfaction with the procedure and recommendation to others summarized by question at the 3-, 6-, 12-, 24-, and 36-month follow-up evaluations.
- Other rhinitis symptoms current symptoms of cough and postnasal drip or excess mucous in the throat, rated on a 0 to 3 scale from 'No symptoms' to 'Severe symptoms', assessed at baseline and the 3-, 6-, 12-, 24-, and 36-month follow-up evaluations.
- Change in amount of PRN medication/device use for chronic rhinitis symptoms - Self-reported assessment of an increase, no change, or decrease in medications being used for treatment of symptoms compared to use prior to the procedure summarized by category at the 3-, 6-, 12-, 24-, and 36month follow-up evaluations.
- Medications Medications associated with relief or treatment of chronic rhinitis symptoms will be documented at baseline and updated as necessary at each evaluation. In addition, medications associated with treatment of adverse events will be documented.

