4.0 Study Plan

4.1 Study Design

The study is designed as a multicenter (up to 20 sites), prospective, open-label, single-arm study in up to 140 participants.

All participants will be evaluated prior to treatment and following treatment at week 13 (3 months). The 3-month evaluation will occur in the physician's office and be used for the primary analysis.

The study will have additional follow-up evaluations at 6, 12, 24, and 36 months conducted by phone interview to provide additional information on longer-term safety and duration of treatment effect.

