No repeat ("touch-up") procedures will be permitted during the study follow-up period.

Procedure data collection

Data relating to the procedure and the products used will be recorded on the Procedure CRF. The following information will be recorded:

• Date of procedure

- Preprocedure nasal assessment (each nostril) including photos or video (physical and endoscopic)
- Preprocedure and procedure medications
- RhinAer Stylus and Aerin Console information
- Aerin Console settings
- Procedure start and end times
- Number of sites treated
- Occurrence of device malfunction, protocol deviation, or adverse events.

5.5 **Postprocedure Assessments and Care**

An endoscopic nasal assessment will be conducted prior to discharging the participant and reported on the Procedure CRF.

Participants will be asked to indicate the pain level experienced during the study procedure from anesthesia delivery to procedure completion using the VAS pain score instrument (vertical line marked on the 100 mm line) on the Pain VAS CRF.

At the discretion of the physician, the following care may be provided:

- Apply compression to the treatment area internally for 5 minutes.
- Apply petroleum jelly to the treatment area as needed.
- Use of nasal saline spray or ointment as needed.
- The participant should be instructed not to blow their nose for 24 hours.

Participants should have their 3-month follow-up visit (13 weeks) scheduled within the visit window prior to release.

Participants should not generally receive other concomitant nasal treatment therapies or interventions after the procedure or during the study follow-up period to avoid confounding the evaluation of the effect of the treatment, unless the additional care is in response to an adverse event or is considered in the best interest of the participant. Therapies, interventions, and pain medication will be monitored at follow-up evaluations.

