5.6 Follow-up Evaluations

Follow-up visit dates will be calculated from the study procedure date. Follow-up visits should be scheduled within the specified visit windows described in Section 5.1 and Table 1 (Section 8.3.2). The office follow-up evaluation occurs at 13 weeks after the procedure. Evaluations at 6, 12, 24, and 36 months will be conducted remotely by telephone assessment by site personnel. The timing of all follow-up evaluations is based on the date of the procedure and should not be altered based on the actual time of preceding follow-up visits. Participants who make nonstudy visits should be evaluated for possible adverse events and an Adverse Event CRF should be submitted if appropriate.

RhinAer RELIEF single arm protocol Rev C Final 27JAN2021CONFIDENTIAL

All participants should be followed through the final evaluation visit at 3 years postprocedure regardless of their success/failure classification at previous evaluations. Every effort should be made to avoid having participants withdraw from the study (Section 9.5). If a participant does choose to withdraw from the study, it is very important to record information regarding the reason(s) and the last known status of the participant.

The following assessments will be conducted as indicated for each follow-up time point and recorded on the corresponding CRFs:

Office evaluation at 13-week (3-month) follow-up

- Nasal assessment (each nostril) including photos or video
- Current use of medication, devices or other therapies for symptoms of chronic rhinitis, including medication name, frequency, and dose
- Participant reported change in use of as needed medications and devices for chronic rhinitis symptoms (completed by participant)
- rTNSS (completed by participant)
- Cough and postnasal drip symptoms (completed by participant)
- MiniRQLQ (completed by participant)
- VAS pain score (completed by participant)
- Adverse events.

Remote (telephone) evaluations: 6-month (26-week), 12-month (52-week), 24-month (104-week), and 36-month (156-week) follow-up

- rTNSS (verbal administration by site personnel)
- Cough and postnasal drip symptoms (verbal administration by site personnel) (no 2-week)
- MiniRQLQ (verbal administration by site personnel)
- Participant reported change in use of as needed medications and devices for chronic rhinitis symptoms (verbal administration by site personnel)
- Patient satisfaction survey (verbal administration by site personnel)

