6.13 Safety Analysis

All adverse events will be analyzed for all participants. Adverse events will be coded using a custom Aerin Medical dictionary so that adverse events may be categorized for analysis at an appropriate level of detail. Listings will be provided to detail individual events. The number of participants, number of AEs, and the proportion of participants reporting each AE will be summarized. Seriousness and severity of AEs and their relationship to the device and procedure will be summarized. A time course of adverse events will be presented. Any unexpected adverse device experiences or adverse events that occur at an unexpectedly high incidence rate will receive detailed analyses. Narratives will be presented for all deaths, serious adverse events, unexpected adverse device experiences, and participants withdrawn due to an adverse event.

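### Adverse event incidence is planned by follow-up intervals of 13 to 52 weeks with no person-time or number-at-risk denominator, so the interval percentages cannot be compared over time

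*Combined protocol and SAP*

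**What the plan says.** Section 3.2 lists adverse events among the informational outcomes, as "Incidence (type and category) of adverse events overall and by follow-up interval"; the Protocol Summary does the same. Section 6.13 says that, besides numbers of participants and of events, "the proportion of participants reporting each AE will be summarized", and that "A time course of adverse events will be presented". It does not define a follow-up interval, say how the time course is built, or name a denominator of person-time or of participants still at risk.

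The intervals have to be read from the schedule. Section 5.6: "The office follow-up evaluation occurs at 13 weeks after the procedure". The Protocol Summary places the later "evaluations conducted at 26 weeks (6 months), 52 weeks (12 months), 104 weeks (24 months) and 156 weeks (36 months)". Section 5.6 adds: "Evaluations at 6, 12, 24, and 36 months will be conducted remotely by telephone assessment by site personnel".

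Adverse events are monitored from enrollment to exit and their onset dates are recorded (7.1.2). Nonstudy visits are also to be checked for events (5.6).

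**The concern.** A percentage of participants with an event depends on how long they were observed. A 52-week interval holds four times the observation time of a 13-week one, so two such percentages describe different quantities even if the underlying rate is the same. Attrition over three years adds to this if the denominator is not the number still under follow-up: the Safety Population in 6.5 is everyone enrolled, treated or not.

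Ascertainment changes as well. Scheduled contacts thin out from 13 weeks apart to 52 weeks apart, so late events rest on longer recall.

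Longer-term safety is a stated reason for the extended follow-up (4.1), and 6.14 stresses summarizing events across the whole study. If the time course is built from raw interval percentages, a reader could not tell a real late change in risk from a longer window, or a real early excess from a shorter one.

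**Working it through.** **Inputs from the documents.** Evaluations at weeks 0 (procedure), 13, 26, 52, 104 and 156. Interval lengths L are the differences: 13, 13, 26, 52 and 52 weeks, or 1, 1, 2, 4 and 4 times the shortest. The plan states no adverse event rate or interval percentage, so there is no figure to reproduce. All rates below are assumptions, shown over a range.

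**1. Constant hazard, complete capture.** Let p be the percentage with at least one event in 13 weeks. The expected percentage in an interval of L weeks is 1 − (1 − p)^(L/13).

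| p per 13 weeks | 0–13 wk | 13–26 wk | 26–52 wk | 52–104 wk | 104–156 wk | last/first |
|---|---|---|---|---|---|---|
| 1% | 1.0 | 1.0 | 2.0 | 3.9 | 3.9 | 3.94 |
| 5% | 5.0 | 5.0 | 9.8 | 18.5 | 18.5 | 3.71 |
| 20% | 20.0 | 20.0 | 36.0 | 59.0 | 59.0 | 2.95 |
| 50% | 50.0 | 50.0 | 75.0 | 93.8 | 93.8 | 1.88 |

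**2. Modest early excess.** Take 8 events per 100 participant-years in the first 13 weeks and 4 afterwards, with percentage 1 − exp(−rate × L/52). The five intervals read 2.0, 1.0, 2.0, 3.9 and 3.9%. The period with twice the rate of year 2 shows half its percentage.

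**3. Larger early excess.** Add an acute procedure-related probability a in weeks 0–13 only, on a background b per 13 weeks, so the first interval is 1 − (1 − a)(1 − b). With b = 2%:

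| a | 0–13 wk | 52–104 wk | last/first |
|---|---|---|---|
| 2% | 4.0 | 7.8 | 1.96 |
| 5% | 6.9 | 7.8 | 1.13 |
| 10% | 11.8 | 7.8 | 0.66 |
| 20% | 21.6 | 7.8 | 0.36 |

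First and last percentages are equal when a = 1 − (1 − b)^3, that is 3.0%, 5.9% or 14.3% for b = 1%, 2% or 5%.

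**4. Recall loss.** If only a fraction c of events is captured over 52 weeks, the ratio is [1 − (1 − b)^(4c)] / b. At b = 2%, c = 75%, 50% and 25% give 2.94, 1.98 and 1.00.

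**5. With person-time.** Under a constant hazard with p = 5% per 13 weeks, the rate is −ln(0.95) × 52/13 × 100 = 20.5 per 100 participant-years, or 20.5/12 = 1.7 per 100 participant-months, in every interval. The raw percentages in the same case run from 5.0 to 18.5.

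**6. Visit windows.** If intervals ran between actual visits, the ±14-day and ±30-day windows would let the second interval last from (182 − 30) − (91 + 14) = 47 days to (182 + 30) − (91 − 14) = 135 days. The bounds therefore need stating as well.

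**The case against.** The strongest reply is that the plan does not commit to a misleading table. Section 6.13 does not tie its proportions to intervals and leaves the time-course method open, and recorded onset dates would allow a person-time display. That is true, but section 3.2 does commit to incidence by interval, and proportions are the only incidence measure that 6.13 names. An open method is a reason to specify it.

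A reader might infer that the percentages must rise about four-fold by construction. The documents do not support this. It needs a constant hazard, low incidence and complete capture. This is a single-session procedure, and section 1.0 describes the related events in the earlier 50-participant study as mild and short-lived, so an early peak is plausible and the series could be flat or fall. Long recall also works against a rise.

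Nor is there just one contact in every interval. That holds for the scheduled calls in the four remote intervals. In the first, events are also collected at the procedure and immediately afterwards; section 5.5 states: "An endoscopic nasal assessment will be conducted prior to discharging the participant and reported on the Procedure CRF". Nonstudy visits can add reports throughout.

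Two limits on the remedy stand. Rates will be imprecise: with 140 participants fully retained, 13 weeks is 35 participant-years, and 2 events there give an exact 95% interval of about 0.7 to 21 per 100 participant-years; 7 events in the 140 participant-years of year 2 give about 2 to 10. And for events on the day of the procedure, the percentage of treated participants is the more natural measure. Rates should therefore stand beside the percentages, not replace them.

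**Conclusion.** The point holds as a gap in the descriptive safety analysis. The scheduled intervals differ by up to a factor of four in length, no exposure or at-risk denominator is planned, and percentages taken from them cannot be compared over time. The factor of four is a fact of the schedule. The ratio of percentages is not fixed: 3.94 to 1.88 under constant hazards of 1% to 50% per 13 weeks, and from 1.96 down to 0.36 once acute events of 2% to 20% are added to a 2% background. All these rates are assumed. The conclusion that survives across them is that neither the size nor the direction of the distortion is known in advance.

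A reader might also infer that the trial's safety conclusion is compromised. It is not. Incidence by interval is informational. The secondary endpoint on related serious adverse events uses one fixed period to 3 months (6.11), and section 3.3 judges safety on overall incidence. What is at stake is the reading of the time course and of the extension-phase safety summary.

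**What to change.** In section 6.13:

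- Define the follow-up intervals by the scheduled visits, counted from the procedure date, and assign each event by its recorded onset date.
- Give the number of participants at risk and the person-time in each interval.
- Report events, and participants with a first event, per 100 participant-months with 95% confidence intervals, beside the counts and percentages. For first events, state whether first means within the interval or within the study, and stop the person-time at that event.
- Note beside the table that events after 6 months are collected at scheduled contacts 6 to 12 months apart, plus any nonstudy visits, so a lower late rate is not by itself evidence of lower risk.

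The cost is SAP wording and a little programming; onset dates are already collected. The downside is wide confidence intervals in the short periods.
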